[figure not shown]
[figure not shown]

NON-INTERVENTIONAL (NI) STUDY PROTOCOL

Study Information

Title	Tofacitinib Use in Rituximab-Experienced RA Patients
Protocol number	A3921420
Protocol version identifier	3.0
Date	13 January 2023
Active substance	Tofacitinib citrate
Medicinal product	Xeljanz
Research question and objectives	
To characterize the use of tofacitinib after use of rituximab in patients with RA in a real-world setting.
 
• Primary: Describe the characteristics of tofacitinib initiators with a history of rituximab exposure, at time of tofacitinib initiation.• Secondary: Describe 6-month outcomes for tofacitinib initiators with a history of rituximab exposure.
Author	PPD Pfizer, Inc PPD
This document contains confidential information belonging to Pfizer. Except as otherwise agreed to in writing, by accepting or reviewing this document, you agree to hold this information in confidence and not copy or disclose it to others (except where required by applicable law) or use it for unauthorized purposes. In the event of any actual or suspected breach of this obligation, Pfizer must be promptly notified.	

PFIZER CONFIDENTIAL

2. LIST OF ABBREVIATIONS

Abbreviation	Term
AE	adverse event
AHRQ	Agency for Healthcare and Research Quality
CDAI	Clinical Disease Activity Index
CDM	Clinical Data Management
CRF	case report form
CSA	Clinical study agreement
DCT	Data collection tool
EDC	Electronic Data Capture
HAQ	Health Assessment Questionnaire
IEC	Independent Ethics Committee
IRB	Institutional Review Board
ISPOR	International Society for Pharmacoeconomics and Outcomes Research
RA	rheumatoid arthritis
RMP	Registry Monitoring Plan
SAP	Statistical Analysis Plan
TB	tuberculosis
TNF	tumor necrosis factor
TNFi	tumor necrosis factor inhibitor
US	United States

4. ABSTRACT

Not Applicable.

[figure not shown]
PFIZER CONFIDENTIAL

5. AMENDMENTS AND UPDATES

Amendment number	Date	Protocol section(s) changed	Summary of amendment(s)	Reason
1.0		Section 9.6.2.	Not applicable, however: To enable evaluations and/or inspections/audits from regulatory authorities or Pfizer, CorEvitas agrees to keep all study-related records. The records should be retained by CorEvitas according to local regulations or as specified in the vendor contract, whichever is longer. CorEvitas must ensure that the records continue to be stored securely for so long as they are retained.	Administrative change: Section 9.6.2. should be deleted for studies with no human review of unstructured data as per CT24 WI-GL02-RF02
1.0	August 4 th Nov 4 th	Section 3.	Job title update and change of 1 Pfizer Principal Investigator Change of 1 Pfizer Principal Investigator	Administrative change: Job position changed, and 1 Pfizer Principal Investigator change
1.0	Nov 11 th	Section 6	Start of data collection	
2.0	13 January 2023	Section 9.1	Language added in the Study Design section.	To clarify that the data analyzed by Pfizer already exists in the CoreVitas registry.
2.0	13 January 2023	Section 3	Added 1 Pfizer Principal Investigator to the list	Administrative change: 1 Pfizer Principal Investigator added.

PFIZER CONFIDENTIAL

6. MILESTONES

Milestone	Planned date
Start of data collection	11 Nov 2022
End of data collection	31 December 2022
Final study report	30 November 2023

7. RATIONALE AND BACKGROUND

Rheumatoid arthritis (RA) is a chronic, immune-mediated, inflammatory disease affecting many joints, including those in the hands and feet. RA has a wide global presence and is estimated to affect 0.5 to 1% of the general population.¹

Some authorities in emerging markets prioritize use of rituximab in treatment of RA because of its relatively lower cost and availability in hospitals. Newer molecules (eg, tofacitinib) usually do not have clinical trial data in rituximab-experienced RA patients. There is a need to understand the use and effectiveness of tofacitinib in the real-world, to provide information for healthcare providers in these emerging market settings.

8. RESEARCH QUESTION AND OBJECTIVES

The objective of this study is to characterize the use of tofacitinib after use of rituximab in patients with RA in a real-world setting.

8.1. Primary Objective(s)

Describe the characteristics of tofacitinib initiators with a history of rituximab exposure, at time of tofacitinib initiation.

8.1.1. Hypotheses

This is a descriptive study without an a priori hypothesis.

8.2. Secondary Objective(s)

Describe 6-month outcomes for tofacitinib initiators with a history of rituximab exposure.

8.2.1. Hypotheses

This study is descriptive with no formal hypothesis, but it is anticipated that outcomes will improve over the 6-month time period.

8.3. Exploratory Objective(s)

None.

9. RESEARCH METHODS

9.1. Study Design

This will be a retrospective analysis of a prospective observational cohort using the CorEvitas RA Registry. This study will evaluate existing data that was previously captured within the registry at the time of study start for analysis, which is specified in the protocol below. This study will describe demographic and clinical characteristics of adult patients with RA initiating tofacitinib with a history of rituximab use. This study will also describe changes in clinical and patient reported outcomes over time. The index date will be defined as the date of tofacitinib initiation at or after enrollment in the registry; initiation is defined as first ever use of tofacitinib.

9.2. Setting

The CorEvitas RA Registry is an ongoing longitudinal clinical registry that was established in 2001. Longitudinal follow-up data is collected from both patients and their treating rheumatologist during routine clinical encounters using the CorEvitas RA Registry questionnaires. These questionnaires collect data on patient demographics, disease duration, medical history (including all prior and current treatments for RA), smoking status, alcohol use, cannabis use, disease activity, patient reported outcome measures, disease characteristics, comorbidities and adverse events, infections, hospitalizations, and other targeted safety outcomes. Blood collection, endoscopy and other diagnostic tests are not required for participation; however, relevant standard of care laboratory and imaging results are reported when available.

9.2.1. Inclusion Criteria

Patients must meet all of the following inclusion criteria to be eligible for inclusion in the study:

Objective 1 Inclusion Criteria:

- Enrolled in the CorEvitas RA Registry and initiated tofacitinib on or after November 2012.
- Initiate tofacitinib (defined as first ever use of tofacitinib) at Registry enrollment visit or at a Registry follow-up visit after November 2012.
- Have prior use of rituximab.
- Have Clinical Disease Activity Index (CDAI) measured at baseline.

Objective 2 Inclusion Criteria:

- Enrolled in the CorEvitas RA Registry and initiated tofacitinib on or after November 2012.

- Initiate tofacitinib (defined as first ever use of tofacitinib) at Registry enrollment visit or at a Registry follow-up, after November 2012.
- Have prior use of rituximab.
- Have CDAI measured at baseline and appropriate follow-up visit.
- Have any of the following:
 - a. A 6-month follow-up visit with persistent use of tofacitinib.
 - b. A 6-month follow-up visit with a tofacitinib discontinuation occurring prior to the 6-month visit, with no new biologic systemic drug used prior to the 6-month study visit.
 - c. A study visit at or prior to the 6-month window with a tofacitinib discontinuation occurring at the study visit.
 - d. (Sensitivity analysis only) Any tofacitinib discontinuation prior to the 6-month study window.

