9.2.2. Exclusion Criteria

There are no exclusion criteria for this study (ie, for either Objective 1 or Objective 2).

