9.4. Data Sources

The CorEvitas RA Registry is an observational registry and therefore collects patient and physician data at patient clinical visits with the rheumatologist. Unlike clinical studies, visits are not timed at exact uniform time periods. Thus, time period definitions for the current study need to accommodate this unique feature of observational registries.

“Index visit” is defined as the visit when tofacitinib was initiated, ie, first ever use of tofacitinib. Only initiations at or after enrollment into the Registry are included.

A “6-month” follow-up is defined as a clinical visit to the rheumatologist 3 to 9 months from the enrollment visit in accordance with the Registry protocol.

Initiations between visits

If tofacitinib is initiated between visits, then baseline variables from the visit prior to the initiation of tofacitinib will be used, as long as the prior visit occurred within four months of the tofacitinib start date. Initiations that occur between visits and where the prior visit is greater than 4 months from the initiation will be excluded.

Multiple visits in the same time window

Given the observational nature of the data, it is possible for patients to have more than one visit that falls within a given follow-up period's allowed time window. For example, a patient might have a visit with outcomes collected at 5 months and then 9 months, both of which would qualify as a "6-month" visit. In that case, the latest visit will be chosen as the "6-month" follow-up since we would like to consider the longest follow-up possible. The exception to this rule is if values for the primary outcome are unavailable for the latest visit, in which case the first visit will be used instead.

Discontinuations prior to follow-up

For patients who discontinued tofacitinib prior to follow-up and who do not switch to another drug, the clinical or patient-reported outcome value at the follow-up visit will be used. If a patient discontinues and switches to another biologic/tsDMARD, the value at the switch visit, if available, will be used; otherwise, the value will be set to missing.

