4.4.3. Time Period Definitions

The CorEvitas RA Registry is an observational registry and therefore collects patient and physician data at patient clinical visits with the rheumatologist. Unlike clinical studies, visits are not timed at exact uniform time periods. Thus, time period definitions for the current study need to accommodate this unique feature of observational registries.

“Index visit” is defined as the visit when tofacitinib was initiated, i.e. first ever use of tofacitinib. Only initiations at or after enrollment into the Registry are included.

A “6-month” follow-up is defined as a clinical visit to the rheumatologist 3 to 9 months from the enrollment visit in accordance with the Registry protocol.

4.4.3.1. *Initiations between visits*

If tofacitinib is initiated between visits, then baseline variables from the visit prior to the initiation of tofacitinib will be used, as long as the prior visit occurred within four months of the tofacitinib start date. Initiations that occur between visits and where the prior visit is greater than 4 months from the initiation will be excluded.

4.4.3.2. *Multiple visits in the same time window*

Given the observational nature of the data, it is possible for patients to have more than one visit that falls within a given follow-up period’s allowed time window. For example, a patient might have a visit with outcomes collected at 5 months and then 9 months, both of which would qualify as a “6-month” visit. In that case, the latest visit will be chosen as the “6-month” follow-up since we would like to consider the longest follow-up possible. The exception to this rule is if values for the primary outcome are unavailable for the latest visit, in which case the first visit will be used instead.

4.4.3.3. *Discontinuations prior to follow-up*

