4.4.7. Analysis Plan

4.4.7.1. Aim 1: *Describe the characteristics of tofacitinib initiators with a history of rituximab exposure, at time of tofacitinib initiation*

Descriptive statistics for the variables listed in [Section 4.4.6](#) will be provided for all tofacitinib initiators with history of rituximab use. All variables will be measured at the index visit, as defined above. Categorical covariates will be described by frequency distribution while continuous covariates will be expressed in terms of their mean and standard deviation or median and interquartile range (IQR) as appropriate.

4.4.7.2. Aim 2: *Describe 6-month outcomes for tofacitinib initiators with a history of rituximab exposure*

Descriptive statistics for index visit characteristics will be provided for the subsets of patients included in this Aim (tfacitinib initiators who have a 6-month follow-up visit), as described in Aim 1.

Analyses of outcomes at the 6-month follow-up after tofacitinib initiation will be descriptive. Primary and secondary outcomes will be described as mean absolute differences for continuous measures and as frequencies and proportions for dichotomous measures, with corresponding 95% confidence intervals (95% CI). Mean absolute difference will be defined as the value at the 6-month follow-up visit minus the value at baseline. The number of patients that discontinue tofacitinib will also be summarized. A subgroup analysis related to the outcomes for Aim 2 will be carried out focused on patients who used rituximab immediately prior to tofacitinib.

All analyses will be conducted using Stata Release 16 (StataCorp LLC, College Station TX) and/or R Version 4.0.3 (The R Foundation for Statistical Computing, Vienna Austria).

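### Protocol 9.2.1 requires tofacitinib to be started at a Registry visit, but Protocol 9.4 and SAP 4.4.3.1 also admit between-visit starts whose prior visit was within four months

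*Protocol*

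**What the plan says.** Protocol 9.2.1 opens its list with "Patients must meet all of the following inclusion criteria to be eligible for inclusion in the study". For Objective 1 one of those criteria is "Initiate tofacitinib (defined as first ever use of tofacitinib) at Registry enrollment visit or at a Registry follow-up visit after November 2012". The matching Objective 2 criterion places the start "at Registry enrollment visit or at a Registry follow-up, after November 2012", so the word *visit* is missing after *follow-up*.

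Protocol 9.2.2 states: "There are no exclusion criteria for this study", and adds that this applies to either objective.

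Protocol 9.4 has a paragraph on starts between visits: "If tofacitinib is initiated between visits, then baseline variables from the visit prior to the initiation of tofacitinib will be used", provided that visit was within four months of the start date. Its last sentence says that initiations between visits "where the prior visit is greater than 4 months from the initiation will be excluded". SAP 4.4.3.1 repeats the paragraph.

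Two places set no visit restriction. Protocol 9.1 defines the index date, and SAP 4.4.2 the primary population, by initiation at or after enrollment.

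On baseline, SAP 4.4.3 says the index visit "is defined as the visit when tofacitinib was initiated", and SAP 4.4.7.1 says "All variables will be measured at the index visit, as defined above".

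**The concern.** The primary objective is to describe a population, so the entry rule largely determines the result. A patient who starts tofacitinib two months after a Registry visit does not meet the Objective 1 criterion as worded, yet Protocol 9.4 gives that same patient a baseline visit and a place in the analysis. Protocol 9.4 itself notes that Registry visits do not fall at uniform times, and both documents give between-visit starts a paragraph, so the authors evidently expected some. Such patients may differ from those who start at a visit. A programmer working from the eligibility list and one working from the between-visit rule could therefore describe different groups.

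A related gap affects Aim 2. The four-month rule sets no condition on other drugs begun between the borrowed visit and the tofacitinib start. Suppose a patient begins another biologic at that visit and starts tofacitinib 3.5 months later. The baseline CDAI then precedes both drugs, and the 6-month change includes the effect of the first. If that drug was rituximab, the patient would also enter the SAP Table 4 subgroup with rituximab as the immediate prior treatment.

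**Working it through.** **Membership by type of start.** Setting the sections side by side:

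| Type of start | Protocol 9.2.1, literal | Protocol 9.4 and SAP 4.4.3.1 | Protocol 9.1 or SAP 4.4.2 read alone |
|---|---|---|---|
| At an enrollment or follow-up visit | in | in | in |
| Between visits, prior visit within four months | out | in | in |
| Between visits, prior visit more than four months earlier | out | out | in |

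Only the second row separates 9.2.1 from 9.4. In the third row both sections leave the patient out. What is wrong there is that 9.4 excludes the patient while 9.2.2 lists no exclusion.

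**Baseline visit.** A between-visit start has no visit at which tofacitinib was initiated, so the SAP 4.4.3 definition does not fit it. SAP 4.4.3.1 does name the visit that supplies baseline variables, and it stands above 4.4.7.1, which refers to definitions above. The term is loose, but the analyst is told which visit to use.

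**The plan's own counts.** Protocol 9.5 and SAP 4.4.9 give feasibility counts from the 31 March 2021 data cut: 390 initiators, ~376 with baseline CDAI, ~373 with line of therapy, and ~107 with CDAI at baseline and 6 months. They are not a calculated sample size and cannot be derived from other inputs. The stated split reproduces: 8 + 365 = 373; 8/373 = 2.1% and 365/373 = 97.9%, against the stated 2% and 98%. Also 376/390 = 96.4% and 107/376 = 28.5%. Nothing in these counts shows how many starts were between visits, or whether any are included.

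**Illustration of size.** Both objectives require baseline CDAI, so the bases are ~376 and ~107, not 390. Assume that the counts do include second-row patients, and that they form the same share f of both cohorts. Literal 9.2.1 then leaves N × (1 − f). At an unchanged SD, the confidence intervals for the 6-month changes widen by a factor of √(1/(1 − f)).

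| f (assumed) | Objective 1, from ~376 | Objective 2, from ~107 | CI width factor |
|---|---|---|---|
| 5% | 357 | 102 | 1.03 |
| 10% | 338 | 96 | 1.05 |
| 20% | 301 | 86 | 1.12 |
| 30% | 263 | 75 | 1.20 |

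For example, at 10%: 376 − 38 = 338, 107 − 11 = 96, and √(1/0.9) = 1.05. If the counts already omit between-visit starts, the table does not apply: the counts would then describe the narrower cohort, and 9.4 would add patients to them.

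**The case against.** The strongest reply is that the documents already settle the matter. Protocol 9.4 and SAP 4.4.3.1 state one specific rule in the same words. Protocol 9.1 and SAP 4.4.2 carry no visit restriction. Protocol 9.7 allows the SAP to modify the protocol's plans. Read literally, 9.2.1 would leave the between-visit paragraph with nothing to do. An analyst would probably apply the four-month rule. All of that stands, and it limits how serious the point is. It does not remove it, because 9.2.1 and 9.4 conflict inside the protocol, and the formal eligibility list would not describe the cohort analysed.

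The Objective 2 bullet, lacking the word *visit*, can be read a little more loosely. It is still the parallel criterion, and SAP 4.4.2 makes Aim 2 a subset of Aim 1.

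It is also fair to say that the drug begun in between is a separate and unusual case with no count in the documents, and that a check for it adds an analytic rule. The four-month rule does leave that case open, however, and dates would identify it.

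A reader might infer that 9.2.2 promises nobody is excluded, and hence that patients in the third row are in under one section and out under another. The documents do not support this. Listing no exclusion criteria does not admit patients who fail an inclusion criterion, and these patients fail 9.2.1 as well as 9.4.

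**Conclusion.** The point holds for one group: between-visit starts whose prior visit was within four months. They are out of both objectives under Protocol 9.2.1 read literally, and in under Protocol 9.4 and SAP 4.4.3.1. The latter rule is probably what was meant. The missing exclusion in 9.2.2 and the index-visit wording in the SAP are matters of labelling and terminology.

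A reader might go further and conclude that the whole cohort for both objectives is undetermined, or that a set number of the 390 would be lost. Neither follows. Starts at a visit are in under every section, the 390 is a feasibility count, and the share of between-visit starts is unknown. The illustrated reductions rest entirely on the assumed shares and on the counts including these patients. No effect on any estimate can be shown from the documents.

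The correction is nonetheless worth making, because it concerns the entry rule of the primary objective. The Aim 2 baseline gap is probably small but could bias the change in CDAI for any patient it touches.

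**What to change.** 1. In Protocol 9.2.1, for both objectives, let the bullet allow a first-ever start *at the enrollment visit, at a follow-up visit, or between visits as defined in 9.4*. The four-month limit then stays in one place.
2. In Protocol 9.2.2, replace the statement that there are none with a cross-reference to the four-month exclusion in 9.4.
3. In SAP 4.4.3, define the index (baseline) visit as the initiation visit or, for between-visit starts, the prior visit allowed by 4.4.3.1.
4. In SAP Figure 1, which is to be populated in the study report, show the between-visit starts kept and those dropped by the four-month rule.
5. For Aim 2, do not use a prior visit as baseline if another bDMARD/tsDMARD was begun at or after that visit and before tofacitinib.

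Items 1 to 4 cost one protocol amendment, matching SAP wording and a flag computed from visit and start dates. Item 5 needs one further date check, and a few patients may lose their Aim 2 baseline.

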9.4.2. Study Outcomes

Objective 1: Characterize Patients at tofacitinib initiation

Primary Outcome:

- Objective 1 is to characterize patients at tofacitinib initiation. All variables as outlined in the SAP will be summarized for this aim.

Objective: Describe change in 6-month outcomes.

Primary Outcome:

- Change in CDAI.

Secondary Outcomes:

- Achievement of Minimum Clinically Important Difference (MCID):² (change in CDAI from baseline to follow-up = Δ CDAI).

CDAI at Index	MCID to Define Improvement in Disease Activity at FU Visit If ΔCDAI>MCID
Low: CDAI \leq 10	1
Moderate: 10 $>$ CDAI \leq 22	6
High $>$ 22	12

- Change in HAQ.
- Change in patient pain.
- Change in patient fatigue.
- Number (%) of tofacitinib discontinuations prior to or at 6-month visit.

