9.5. Study Size

As of the 31 March 2021 data cut, there were 390 tofacitinib initiators with history of rituximab use. Of these:

- ~376 have baseline CDAI information.
- Line of therapy (and baseline CDAI) is available for ~373, of whom n=8 (2%) are 3rd line and n=365 (98%) are 4th line.
 - Note: since population is restricted to those with prior rituximab use, 3rd line use reflects patients with prior rituximab use only 4th line reflects patients with one or more prior biologic in addition to rituximab.
- ~107 have CDAI information at baseline and 6 months follow-up.

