4.4.8. Missing Data

Missing data could be expected for demographic characteristics (e.g., age, etc.); however, the number of patients with missing data is expected to be very small, and is not expected to vary systematically. For every variable, the number of patients with nonmissing information will be reported. Effective sample size may differ across outcome measures due to missingness; because missingness is expected to be very minimal, no imputation of missing values will be applied.

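### Objective 2 requires a follow-up CDAI even for outcomes that do not use it, above all the discontinuation percentage, and the SAP neither repeats nor lifts that condition

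*Protocol*

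**What the plan says.** Protocol 9.2.1 opens with a general rule: "Patients must meet all of the following inclusion criteria to be eligible for inclusion in the study". The Objective 2 list then includes "Have CDAI measured at baseline and appropriate follow-up visit", with no restriction to particular outcomes. Beside it stand four visit or discontinuation routes, a to d, of which d is for a sensitivity analysis only. Objective 1 has its own, separate requirement of a baseline CDAI.

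Protocol 9.4.2 lists six outcomes for the six-month objective. Two are built on CDAI: its change, and achievement of the minimum clinically important difference (MCID). The other four are the changes in HAQ, pain and fatigue, and "Number (%) of tofacitinib discontinuations prior to or at 6-month visit".

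The SAP words the population differently. Section 4.4.2 makes Aim 2 a subset of the primary analysis with a six-month visit that carries clinical and patient-reported data; it does not mention CDAI. Section 4.4.8 says "Effective sample size may differ across outcome measures due to missingness" and promises a non-missing count for every variable. The Table 3 shell has a single N, while Table 4 has an N column. Neither has a row for discontinuation, although SAP 4.4.7.2 says that the number of patients who discontinue will be summarised.

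The only Objective 2 size in either document (Protocol 9.5, repeated in SAP 4.4.9) is that about "107 have CDAI information at baseline and 6 months follow-up".

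**The concern.** HAQ, pain and fatigue come from patient questionnaires, and discontinuation comes from the treatment record. SAP 4.4.6.4 and 4.4.6.5 themselves separate the physician-derived measures, where CDAI sits, from the patient-reported ones, so one can be missing while the other is present. As the protocol is written, a patient in that position drops out of all six results.

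For the three patient-reported changes, the stake is mainly a few lost observations. Discontinuation is different. The percentage is conditioned on a measurement taken after baseline, and whether that measurement is made could be related to stopping. Protocol 9.9 names differences between patients who stay on treatment and patients who stop as a source of bias and says that steps are taken to reduce it. A CDAI condition on who is counted works against that aim. The SAP's current analysis plan also contains no sensitivity analysis for Aim 2 that would show the effect.

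Separately, an analyst with both documents cannot tell whether the Objective 2 set is CDAI-complete (protocol) or varies by outcome (one reading of the SAP).

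**Working it through.** **Inputs from the documents (Protocol 9.5).** There are 390 initiators with prior rituximab, about 376 with a baseline CDAI, and about 107 with CDAI at both times. These are registry counts, so there is no sample-size formula to reproduce. The line-of-therapy figures in the same section are consistent: 8 + 365 = 373, 8/373 = 2.1% and 365/373 = 97.9%, matching the stated 2% and 98%.

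**Step 1: which exclusions belong to the follow-up condition.** Baseline CDAI is missing in 390 − 376 = 14 patients, 14/390 = 3.6%. Objective 1 excludes these patients, and SAP 4.4.2 makes Aim 2 a subset of the primary analysis, so they are out whatever the Objective 2 bullet says. Only a missing follow-up CDAI is attributable to that bullet.

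**Step 2: patients lost.** Let f be the share of otherwise eligible primary-cohort patients who lack only a follow-up CDAI. The documents do not give f. The full set is n = 107/(1 − f). The 95% half-width for a proportion near 50% is 1.96 × √(0.25/n).

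| Assumed f | n | Patients regained | Half-width (points) |
|---|---|---|---|
| 0 | 107 | 0 | 9.5 |
| 3.6% | 111 | 4 | 9.3 |
| 10% | 119 | 12 | 9.0 |
| 20% | 134 | 27 | 8.5 |

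The 3.6% row borrows the baseline missing rate. The others show how the answer moves. The gain in precision is small throughout. For a mean change, the half-width is 1.96/√n in SD units: 0.19 SD at both n = 107 and n = 111.

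**Step 3: discontinuation.** Let p be the proportion stopping among CDAI-complete patients and q the proportion among those excluded only for follow-up CDAI. The full-set proportion is (1 − f)p + fq, which equals p when q = p. So there is no bias unless stopping differs between patients with and without a follow-up CDAI. Taking p = 30% purely as an assumption:

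| f | q = 0 | q = 30% | q = 60% | q = 100% |
|---|---|---|---|---|
| 3.6% | 28.9% | 30.0% | 31.1% | 32.5% |
| 10% | 27.0% | 30.0% | 33.0% | 37.0% |

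At f = 3.6% even the extreme values of q move the figure by 2.5 points or less. Neither p, q nor f has a source in the documents.

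**Step 4: does the SAP lift the condition?** SAP 4.4.2 does not mention CDAI, but it does not withdraw the protocol criterion either. Its call for clinical as well as patient-reported data could even be read as requiring a clinical measure. SAP 4.4.8 allows n to vary, but n can also vary inside a CDAI-complete set. The SAP's amendment table records no change to this criterion, and no other denominator for discontinuation is defined.

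**The case against.** The strongest reply has four parts.

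**The SAP governs.** Protocol 9.7 lets the SAP modify protocol plans, and the SAP was last amended after the current protocol. On this view its silence about CDAI means outcome-specific denominators. That reading is possible but not stated, so the need to reconcile the texts stands.

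**One cohort is a reasonable choice.** In a descriptive study, a single set anchored on the primary outcome lets every row describe the same patients. For HAQ, pain and fatigue this is a genuine trade-off, although the documents do not give it as their reason. It does not justify requiring a CDAI before a stop is counted.

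**Little is lost.** SAP 4.4.8 expects very little missingness, and physician and patient data are collected at the same office visit (SAP 4.4.1). If the latest in-window visit lacks the primary outcome, the first is used instead (Protocol 9.4, SAP 4.4.3.2). This stands as an argument about size.

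**Stops are not generally lost at unscored visits.** A reader might infer that any stop at a visit without a CDAI goes uncounted. That fits mainly route c. Under route b the stop comes before the six-month visit, and the CDAI is needed at follow-up. SAP 4.4.3.3 carries forward the preceding registry visit for stops between visits.

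**Conclusion.** The point holds as a matter of wording and avoidable selection, with a probably small and unquantified effect. Protocol 9.2.1 applies the follow-up CDAI condition to four outcomes that do not need it, the SAP is worded differently without lifting it, and the discontinuation percentage has no other defined denominator. At an assumed 3.6% missing follow-up CDAI, about 4 patients are lost (107 against about 111).

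Three stronger readings are not supported:

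- A reader might take the fall from 376 to 107, 269 patients, as the loss. That figure mixes patients with no qualifying visit and patients with a visit but no CDAI, and the documents do not separate them.
- A reader might apply 3.6% at both baseline and follow-up and conclude that about 7% are lost (107/0.964² = about 115). The baseline part is already excluded under Objective 1.
- A reader might conclude that discontinuation is understated. That would require CDAI to be missing more often in patients who stop, and nothing in the documents shows this.

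**What to change.** 1. In Protocol 9.2.1, Objective 2, keep the baseline CDAI requirement so that Objective 2 remains a subset of the Objective 1 cohort. Limit the follow-up CDAI requirement to change in CDAI and MCID.
2. Report discontinuation for all primary-cohort patients meeting the visit or discontinuation criteria, whether or not a follow-up CDAI was recorded. Give it a row in Table 3 with its own denominator.
3. Report HAQ, pain and fatigue on patients with that measure at both times, with n per row in Table 3 as in Table 4. The CDAI-complete set can be shown as well for comparability.
4. State the same populations in SAP 4.4.2, and say which in-window visit supplies the non-CDAI outcomes when none has a CDAI.

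The cost is one reworded bullet, a matching sentence or two in the SAP, and a row and a column in Table 3. No new data are needed, because the registry data already exist (Protocol 9.1). Row Ns will differ, which SAP 4.4.8 already accepts, and the subset column of Table 1 should be labelled with the set it describes.

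This does not remove the selection made by routes a to c themselves. Some patients who stop between visits qualify only under route d, which the protocol reserves for a sensitivity analysis that the current SAP no longer contains. The discontinuation row should state that limit.
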